The patient should be observed for 60 minutes following the first infusion of SGN-35. During this observation period, the IV line should remain open for at least 1 hour to allow administration of IV drugs if necessary. All supportive measures consistent with optimal patient care will be given throughout the treatment according to institution standards. Medications for infusion-related reactions, such as epinephrine, antihistamines, and corticosteroids, should be available for immediate use.

A patient who experiences a Grade 1 or Grade 2 infusion-related reaction may receive subsequent SGN-35 infusions with premedication consisting of acetaminophen (650 mg orally) and diphenhydramine (25-50 mg orally or 10-25 mg IV) or according to institutional standards, administered 30-60 minutes prior to each 30-minute SGN-35 infusion. The routine use of steroids as premedication is discouraged.

Dose Modifications

Intrapatient dose reduction to 0.8 mg/kg will be allowed depending on the type and severity of toxicity. The following table describes the recommended dose modifications for study treatment-associated toxicity.

The start of the next cycle may be delayed for up to 3 weeks if additional time is required for the patient to recover from study treatment-associated toxicity experienced during the current cycle. Doses reduced for drug-related toxicity should generally not be re-escalated. However, intrapatient re-escalation to the previous dose level may be permitted at the discretion of the treating physician.

Toxicity	Grade 1	Grade 2	Grade 3	Grade 4
Non-hematologic	Continue at same dose level.	Continue at same dose level, except in the event of Grade 2 neuropathy. For Grade 2 neuropathy, reduce dose to 0.8mg/kg. For the second occurrence of Grade 2 neuropathy, withhold dose until toxicity is \leq Grade 1 or has returned to baseline, then resume at 0.8 mg/kg.	Withhold dose until toxicity is \leq Grade 1 or has returned to baseline, then resume treatment at the same dose level ^a . For Grade 3 or higher neuropathy, discontinue treatment at the discretion of the investigator.	Withhold dose until toxicity is \leq Grade 1 or has returned to baseline, then reduce dose to 0.8 mg/kg and resume treatment, or discontinue at the discretion of the investigator ^a .

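### For a patient still on 1.2 mg/kg who continues after grade 3 neuropathy, the dose table does not recommend 0.8 mg/kg, the dose it sets after grade 2 neuropathy

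*Combined protocol and SAP*

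**What the plan says.** The dose rules are in section 5.0 under Dose Modifications. The starting dose is 1.2 mg/kg and there is one reduced level. The text above the table says "Intrapatient dose reduction to 0.8 mg/kg will be allowed depending on the type and severity of toxicity" and introduces the table with "The following table describes the recommended dose modifications for study treatment-associated toxicity". It also says "Doses reduced for drug-related toxicity should generally not be re-escalated", though the treating physician may permit re-escalation, and "The start of the next cycle may be delayed for up to 3 weeks" to allow recovery.

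The non-hematologic row then reads as follows.

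- **Grade 2.** Same dose, with neuropathy excepted: "For Grade 2 neuropathy, reduce dose to 0.8mg/kg". A second grade 2 neuropathy is held until grade 1 or less, or baseline, and restarted at 0.8 mg/kg.
- **Grade 3.** Hold until grade 1 or less, or baseline, "then resume treatment at the same dose level". A further sentence follows: "For Grade 3 or higher neuropathy, discontinue treatment at the discretion of the investigator".
- **Grade 4.** Hold to the same recovery threshold, "then reduce dose to 0.8 mg/kg and resume treatment, or discontinue at the discretion of the investigator".

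**The concern.** Neuropathy is taken out of the same-dose rule at grade 2, but the grade 3 cell makes no corresponding change to the restart dose. It makes stopping discretionary and does not mention 0.8 mg/kg. An investigator who keeps a patient on drug and follows the cell as written could therefore restart at a higher dose than the table recommends after a milder event.

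The restart dose matters for this toxicity in particular. Section 3.0 reports dose-related neuropathy in the every-3-week phase I study, and section 14.0 makes grade 3 or higher neuropathy in 5 of the first 18 patients the toxicity stopping criterion. The expansion cohort plans nine doses instead of six and refers to the same section 5.0 for dosing.

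**Working it through.** The plan gives no figure to reproduce. The check is a side-by-side reading of the table, followed by simple arithmetic.

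**Step 1. Dose per infusion if treatment continues, for a patient on 1.2 mg/kg at the time of the event**

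| Event | Hold first? | Restart dose in the table |
|---|---|---|
| Grade 2 neuropathy, first | No | 0.8 mg/kg |
| Grade 3 neuropathy, general rule of the cell still applies | Yes, to grade 1 or less or baseline | 1.2 mg/kg |
| Grade 3 neuropathy, neuropathy sentence replaces the general rule | Not stated | None recommended; 0.8 mg/kg permitted by the text above the table |
| Grade 4 non-hematologic | Yes, same threshold | 0.8 mg/kg, or discontinue |

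A second grade 2 neuropathy is held to the same threshold and resumes at 0.8 mg/kg. A patient already reduced to 0.8 mg/kg who then has grade 3 neuropathy resumes at 0.8 mg/kg, because that is the same dose level.

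**Step 2. Size of the difference under the first grade 3 reading**

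- Per dose: 1.2 − 0.8 = 0.4 mg/kg; 0.4 / 0.8 = 50%.
- Per cycle with no dose omitted: 3 × 1.2 = 3.6 against 3 × 0.8 = 2.4 mg/kg.
- If the hold costs one dose in the cycle: 2 × 1.2 = 2.4 mg/kg, equal to three doses at 0.8. If it costs two: 1 × 1.2 = 1.2 mg/kg, which is less.

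The difference per restarted dose is therefore fixed, but the difference in total exposure is not.

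**Step 3. Time available for a restart**

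Doses are on days 1, 8 and 15 of 28-day cycles (sections 4.2 and 4.2.1). After an event at the day 15 dose of cycle 1, cycle 2 is due on day 29 and may start up to 21 days late: (29 + 21) − 15 = 35 days to recover. An event after the last planned dose leads to no restart.

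Latest last dose, if every later cycle starts 21 days late and doses within cycles are on time:

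- Main cohort: 43 + 21 = day 64 (2.1 months).
- Expansion: 71 + 2 × 21 = day 113 (3.7 months).

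**Step 4. How many patients**

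Section 3.0 reports that the weekly phase I study enrolled 44 patients and that 5 had grade 3 neuropathy: 5/44 = 11.4%. Three were motor neuropathies after 4 to 9 months of treatment, later than either cohort's last dose. The timing of the other two is not given.

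Assumption: the phase I rate carries over, and between none and both of those two cases arose early enough to count. This gives 0/44 to 2/44, or 0 to 4.5%.

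- Main cohort: 46 × 2/44 = 2.1, so about 0 to 2 of 46.
- Expansion: 20 × 2/44 = 0.9, so about 0 to 1 of 20.

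These counts come before removing patients who stop, do not recover in time, or are already on 0.8 mg/kg. They are imprecise: the exact (Clopper-Pearson) 95% interval for 2/44 is 0.6 to 15.5%, and its upper end would be 46 × 0.155 = 7.1 and 20 × 0.155 = 3.1 patients before the same removals.

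**The case against.** The strongest reply is that the specific sentence should govern. The only action it names for grade 3 or higher neuropathy is discontinuation, so the neuropathy sequence is continue, reduce, stop, which rises in order. The table is only recommended, 0.8 mg/kg is expressly allowed, and section 13.0 removes patients with unacceptable toxicity. A patient seen at every weekly dose may also pass through grade 2 and already be on 0.8 mg/kg.

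Much of this stands. It rules out three stronger conclusions that a reader might draw:

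- **That no usable dose exists if the specific sentence governs.** The text above the table permits 0.8 mg/kg. What is missing is a recommendation.
- **That the plan gives more drug overall after worse neuropathy.** This holds per restarted dose, but not necessarily in total once held doses are counted (step 2).
- **That 0.8 mg/kg can never follow grade 3 neuropathy.** It does for patients already reduced, and an investigator may choose it for others.

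The evidence on dose is also limited. The dose-related finding comes from every-3-week dosing at 0.1 to 3.6 mg/kg, and the documents do not compare 1.2 with 0.8 mg/kg weekly after recovery. The choice of 0.8 mg/kg rests on consistency with the rest of the table and on clinical judgement.

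The reply does not close the gap. Stopping is discretionary, so the option of continuing needs a dose. Unacceptable toxicity is not defined as grade 3 neuropathy. The required hold does not explain a higher restart dose either, since a second grade 2 neuropathy is held to the same threshold and restarts at 0.8 mg/kg.

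**Conclusion.** The point holds for patients still on 1.2 mg/kg who are kept on treatment after grade 3 neuropathy. For them the grade 3 cell either restarts at 1.2 mg/kg, 50% above the per-dose level recommended after a first or second grade 2 neuropathy, or recommends no restart dose. In neither case does it recommend 0.8 mg/kg, and the documents give no reason for the difference.

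The reach is small: about 0 to 2 of 46 and 0 to 1 of 20 patients before further exclusions, and possibly none. That range assumes that the phase I rate carries over and that only its two cases of unstated timing could fall within the treatment period.

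A reader might infer from the role of grade 3 neuropathy in section 14.0 that the stopping rule or the efficacy conclusions are affected. The documents do not support that. The rule counts patients who have had the event, and the restart dose enters no sample size, error rate or primary analysis. This is a correctable gap in a safety instruction and should be fixed.

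**What to change.** In the grade 3 non-hematologic cell, except neuropathy from the same-dose rule and replace its neuropathy sentence with: *For Grade 3 neuropathy, discontinue; if the investigator elects to continue, withhold until Grade 1 or less or baseline, then resume at 0.8 mg/kg.* Grade 4 neuropathy stays under the grade 4 cell, which already gives 0.8 mg/kg after recovery or discontinuation. The sponsor's clinicians may prefer to make discontinuation mandatory, which would also close the gap.

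The cost is a wording change to one cell that serves both cohorts. The downside is a lower dose for the rare patient who continues after grade 3 neuropathy.

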6.0 CRITERIA FOR SUBJECT ELIGIBILITY

6.1 Subject Inclusion Criteria

- Histologic diagnosis of cd30 positive classical Hodgkin's lymphoma.
- Primary refractory or relapsed disease proven by biopsy or fine needle aspiration (cytology) of an involved site. Pathology must be reviewed at MSKCC.

- Relapse or refractory disease following doxorubicin or nitrogen mustard containing front-line therapy
- Fluorodeoxyglucose (FDG)-avid disease by FDG-PET/CT and measurable disease of at least 1.5 cm by spiral CT, as assessed by the site radiologist.
- Cardiac ejection fraction of greater than 45%, measured since last chemotherapy.
- Hemoglobin-adjusted diffusing capacity for carbon monoxide of greater than 50% on pulmonary function testing, measured since last chemotherapy
- Serum creatinine ≤ 1.5 mg/dl; if creatinine > 1.5 mg/dl then the measured 12- or 24-hour creatinine clearance must be > 60 ml/minute.
- ANC $> 1000/\mu\text{l}$ and Platelets $> 50,000/\mu\text{l}$
- Total bilirubin < 2.0 mg/dl in the absence of a history of Gilbert's disease.
- Females of childbearing age must be on an acceptable form of birth control.
- Age between 12 and 72
- HIV I and II negative.

6.2 Subject Exclusion Criteria

- Received more than 1 prior treatment (combined modality therapy represents 1 treatment) for Hodgkin Lymphoma
- Hepatitis B surface antigen positive or hepatitis B core antibody positive.
- Known pregnancy or breast-feeding.
- Medical illness unrelated to Hodgkin's Lymphoma, which, in the opinion of the attending physician and/or principal investigator, makes participation in this study inappropriate.
- Peripheral neuropathy $>$ grade 1

7.0 RECRUITMENT PLAN

Patients seen in the inpatient or outpatient setting who meet eligibility criteria will be recruited to this study. An attending physician of the Lymphoma or Hematology service will evaluate all patients.

8.0 PRETREATMENT EVALUATION

Prior to initiating treatment:

- Obtain tissue blocks or unstained slides (10) to confirm relapsed or refractory disease and to stain for CD68, TIA-1, and FOXP3
- Obtain tissue block or unstained slides (10) from initial diagnostic biopsy to stain for CD68, TIA-1, and FOXP3

- Bone marrow biopsy to be performed after the most recent treatment for Hodgkin lymphoma. Bilateral bone marrow biopsies to be performed if previously positive unless there was a bone marrow biopsy performed since the last treatment that was positive (then the unilateral bone marrow biopsy is sufficient).

Within 2 weeks prior to initiating treatment:

- CBC
- ESR
- Electrolytes (Na, K, Cl, CO₂), BUN, Cr, bilirubin, total protein, albumin, AST, ALT, alkaline phosphatase, uric acid, and LDH
- Hemoglobin (Hgb) A1c
- Serum β -HCG (premenopausal females only) to assess for pregnancy
- Creatinine clearance by 12- or 24-hr urine collection if serum Cr>1.5 mg/dl
- Modified Total Neuropathy Score (mTNS) and European Organization for Research and Treatment of Cancer (EORTC) quality of life questionnaire for chemotherapy-induced peripheral neuropathy (CIPN-20)

Within 4 weeks prior to initiating treatment:

- CT scan of the chest, abdomen, and pelvis
- ¹⁸F-fluorodeoxyglucose-PET/CT scan
- Echocardiogram or MUGA scan
- Pulmonary Function Testing

Within 6 months of initiating treatment

- Hepatitis B surface antigen
- Hepatitis B core antibody
- Hepatitis C serology
- HIV I/II antibodies

9.0 TREATMENT/INTERVENTION PLAN

Patients will receive 2 cycles of weekly brentuximab vedotin, 1.2mg/kg on days 1, 8, and 15 of each 28 day cycle. See section 5.0 for dosing and administration of brentuximab vedotin. FDG-PET/CT will be repeated after 2 cycles of treatment within 1 week of the last dose of cycle 2. Patients with pre-treatment positive bone marrow biopsies will have repeat bone marrow biopsies if the PET scan is negative. Patients with normalization of FDG-PET/CT

and negative bone marrow biopsies after brentuximab vedotin will proceed to arm A. Patients with persistent FDG-PET/CT abnormalities will proceed to arm B.

Arm A: Patients with negative FDG-PET/CT following 2 cycles of brentuximab vedotin will undergo stem cell mobilization in preparation for ASCT.

Stem cell mobilization and collection will be performed as per standard MSKCC guidelines.

Arm B: Patients with persistent abnormalities on FDG-PET/CT following 2 cycles of brentuximab vedotin will receive 2 cycles of augmented ICE. The first cycle of augmented ICE will be initiated 7-14 days after the last dose of SGN-35. FDG-PET/CT will be repeated within 21 following the second cycle of augmented ICE. Stem cell mobilization can be performed following the first or second cycle of augmented ICE.

Augmented ICE will be administered as follows:

Ifosfamide (5,000 mg/m²) mixed with Mesna (5,000 mg/m²) IVCI x 2 starting on day 1

Carboplatin (AUC 5 [maximum dose 800 mg]) IVPB x 1 on day 3

Etoposide (200 mg/m²) IVPB Q 12 hours x 3 doses starting on day 1

The second cycle of augmented ICE will be initiated no sooner than 17 days after the first cycle. ANC must be $\geq 1000/\mu\text{l}$ and platelet count must be $\geq 50,000/\mu\text{l}$ for ICE to be administered. Treatment will be held until these criteria are met. No dose reductions will be allowed.

For **non-collection cycles**, either pegfilgrastim 6 mg on day after hospital discharge (completion of chemotherapy) or filgrastim 300 mcg (for patients under 70 kg) or 480 mcg (for patients over 70 kg) on days +5 to +12 will be given.

For **collection cycles**, Filgrastim at 10 mcg/kg/day will be given on day +5 and continue until stem cell collection completed (approximated to the nearest increment of Filgrastim 600 mcg, 780 mcg, 960 mcg, 1260 mcg, or 1,440 mcg).

Stem cell mobilization and collection will be performed as per standard MSKCC guidelines.

Pediatric patients will be treated in the Pediatric Day Hospital.

9.0.1 EXPANSION COHORT: TREATMENT INTERVENTION/PLAN

Patients will receive 3 cycles of weekly brentuximab vedotin, 1.2mg/kg on days 1, 8, and 15 of each 28 day cycle. See section 5.0 for dosing and administration of brentuximab vedotin. FDG-PET/CT will be repeated after 3 cycles of treatment within 1 week of the last dose of cycle 3. Patients with pre-treatment positive bone marrow biopsies will have repeat bone marrow biopsies if the PET scan is negative. Patients with normalization of FDG-PET/CT and negative bone marrow biopsies after brentuximab vedotin will proceed to arm A. Patients with persistent FDG-PET/CT abnormalities will proceed to arm B.

Arm A: Patients with negative FDG-PET/CT following 3 cycles of brentuximab vedotin will undergo stem cell mobilization in preparation for ASCT.

Stem cell mobilization and collection will be performed as per standard MSKCC guidelines.

Arm B: Patients with persistent abnormalities on FDG-PET/CT following 3 cycles of brentuximab vedotin will receive 2 cycles of augmented ICE. The first cycle of augmented ICE will be initiated 7-14 days after the last dose of SGN-35. FDG-PET/CT will be repeated within 21 days following the second cycle of augmented ICE. Stem cell mobilization can be performed following the first or second cycle of augmented ICE.

Augmented ICE will be administered as follows:

Ifosfamide (5,000 mg/m²) mixed with Mesna (5,000 mg/m²) IVCI x 2 starting on day 1
Carboplatin (AUC 5 [maximum dose 800 mg]) IVPB x 1 on day 3
Etoposide (200 mg/m²) IVPB Q 12 hours x 3 doses starting on day 1

The second cycle of augmented ICE will be initiated no sooner than 17 days after the first cycle. ANC must be \geq 1000/ μ l and platelet count must be \geq 50,000/ μ l for ICE to be administered. Treatment will be held until these criteria are met. No dose reductions will be allowed.

For **non-collection cycles**, either pegfilgrastim 6 mg on day after hospital discharge (completion of chemotherapy) or filgrastim 300 mcg (for patients under 70 kg) or 480 mcg (for patients over 70 kg) on days +5 to +12 will be given.

For **collection cycles**, Filgrastim at 10 mcg/kg/day will be given on day +5 and continue until stem cell collection completed (approximated to the nearest increment of Filgrastim 600 mcg, 780 mcg, 960 mcg, 1260 mcg, or 1,440 mcg).

Stem cell mobilization and collection will be performed as per standard MSKCC guidelines.

Pediatric patients will be treated in the Pediatric Day Hospital.

10.0 EVALUATION DURING TREATMENT/INTERVENTION

Tests to be performed day 1 of each cycle of brentuximab vedotin

- History and physical exam
- CBC (may be drawn within 24 hours pre-treatment)
- Comprehensive metabolic panel
- ESR
- Cytokine levels (one 8.5 mL SST speckled red top tube - IL-10, IL-6, IL-1, TNF α):
*****cycle 1 only**
- Modified Total Neuropathy Score (mTNS) and European Organization for Research and Treatment of Cancer (EORTC) quality of life questionnaire for chemotherapy-induced peripheral neuropathy (CIPN-20): *****cycle 2 only**

Tests to be performed day 8 and 15 of each cycle of brentuximab vedotin

- History and physical exam
- CBC (may be drawn within 24 hours pre-treatment)

Tests to be performed at the completion of 2 cycles of brentuximab vedotin:

- FDG-PET/CT (1-7 days after the last dose of brentuximab vedotin, between days 44 and 50). All studies will be obtained on dedicated PET/CT cameras. Patients must fast for 6 hrs prior to PET imaging, but intake of water or other non-caloric beverages is encouraged. When the patient arrives at one of the nuclear medicine imaging sites, a fingerstick blood glucose measurement will be obtained; patient with blood glucose levels > 200mg/dl are ineligible. Approximately 12 mCi of 18F FDG will be injected intravenously. Following an approximately 60-80 min uptake time, CT and PET images will be obtained from skull base to upper thigh using standard clinical imaging protocols. For a given patient, all serial PET/CT scans will be obtained on the same camera model.
- CT chest, abdomen, pelvis (1-7 days after the last dose of brentuximab vedotin, between days 44 and 50)

Within 1 week of last dose of SGN-35 (+/- 4 days)

- Hemoglobin A1c
- Cytokine levels (one 8.5 mL SST speckled red top tube - IL-10, IL-6, IL-1, TNF α)
- Modified Total Neuropathy Score (mTNS) and European Organization for Research and Treatment of Cancer (EORTC) quality of life questionnaire for chemotherapy-induced peripheral neuropathy (CIPN-20)
- Bone marrow biopsy (if BM was involved before treatment and post-SGN-35 PET scan is negative)

Interventions while receiving brentuximab vedotin (SGN-35)

Treatment days

Test/treatment	Pretreatment	1	8	15	22	29	36	43	44-50
SGN-35		x	x	x		x	x	x	
History and Physical		x	x	x		x	x	x	
CBC	x	x*	x*	x*		x*	x*	x*	
Comprehensive Metabolic Panel	x	x				x			
ESR	x	x				x			
Uric acid	x								
Lactate dehydrogenase	x								
Creatinine clearance**	x								

Hemoglobin A1c	x								x
Serum β -HCG***	x								
Hep B, C, HIV	x								
Cytokines		x							x
Neuropathy Questionnaire	x					x			x
BM Bx	x								****
FDG-PET/CT and CT CAP	x								x
Echo or MUGA	x								
PFTs	x								

*may be drawn within 24 hours pre-treatment; ** if creatinine >1.5; ***premenopausal females; ****if previously positive

The following applies to patients receiving augmented ICE:

- A CBC and basic metabolic panel will be obtained upon each admission for chemotherapy and a 12-hour urine collection for creatinine clearance will be obtained prior to receiving carboplatin. Other laboratory evaluations during admission for ICE chemotherapy may be performed at the discretion of the inpatient attending physician. When receiving ifosfamide, urine will be monitored for hematuria by urinalysis.

The following will be performed within 21 days following the completion of augmented ICE:

- CT scan of the chest, abdomen, and pelvis
- FDG-PET/CT scan
- Bone marrow biopsy (if BM was involved before treatment and post-ICE PET scan is negative)

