The second phase I study evaluated weekly administration of brentuximab vedotin (day 1, 8, and 15 of 28 day cycles)⁹. The study enrolled 44 patients, 86% with HL. The maximum tolerated dose was determined to be 1.2mg/kg and the dose limiting toxicities were diarrhea and hyperglycemia. The incidence of peripheral neuropathy seen with this dosing schedule

was similar to that seen with every 3 week dosing. About 50% of patients experienced peripheral neuropathy, mostly grade 1 or 2. Five patients experienced grade 3 peripheral neuropathy, 3 with motor neuropathies after 4-9 months of treatment with brentuximab vedotin. Thirteen CRs and 9 PRs were seen with an overall response rate of 56%. Most notable was that the majority of the complete responses were seen at the first restaging performed 8 weeks into treatment (following 2 cycles). The tolerability, efficacy, and early responses seen with this dosing schedule make this an attractive agent to test as a salvage therapy prior to ASCT in rel/ref HL.

Rationale for salvage therapy with brentuximab vedotin

Standard salvage regimens administered before ASCT, such as ICE or DHAP, are inpatient therapies, associated with significant hematologic toxicity, and risk of myelodysplastic syndrome and infertility. A therapy that is less toxic but can still achieve the same rate of response is desirable. In particular, avoiding ICE chemotherapy, but achieving a similar rate of chemosensitivity using less toxic therapy would be considered a success. Weekly brentuximab vedotin is an attractive regimen to test in this setting because it is associated with encouraging response rates, and complete responses are seen after only 8 weeks, which is desirable for a salvage therapy leading to ASCT. In this study, transplant-eligible patients with rel/ref HL will receive 2 cycles of weekly brentuximab vedotin. FDG-PET/CT will be performed following 2 cycles and patients with PET-normalization will proceed to transplant. Patients with persistent abnormalities on FDG-PET/CT will receive standard salvage treatment with 2 cycles of augmented ICE chemotherapy prior to proceeding to ASCT.

Rationale for expansion cohort in patients who fail front-line therapy with brentuximab vedotin

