Hematologic	Continue at same dose level.	Continue at same dose level.	Withhold dose until toxicity is \leq Grade 2, or has returned to baseline, then resume treatment at the same dose level ^b . Consider growth factor support (G-CSF or GM-CSF) for treatment of neutropenia and prophylaxis in subsequent cycles.	Withhold dose until toxicity is \leq Grade 2, then resume treatment at the same dose level. Consider growth factor support (G-CSF or GM-CSF) for treatment of neutropenia and prophylaxis in subsequent cycles. For the second occurrence of Grade 4 toxicity (if neutropenia, while receiving growth factor support), withhold dose until toxicity is \leq Grade 2, then reduce the dose to 0.8 mg/kg and resume treatment ^b .

- a. Patients who develop Grade 3 or 4 electrolyte laboratory abnormalities may continue study treatment without interruption.
- b. Patients who develop Grade 3 or 4 lymphopenia may continue study treatment without interruption.

Storage and Handling

Vials containing SGN-35 must be refrigerated at 2-8°C in an appropriate locked room accessible only to the pharmacist, the investigator, or a duly designated person.

Reconstituted SGN-35 should not be stored at room temperature. The effect of light on SGN-35 has not been assessed; therefore, it is recommended that SGN-35 vials and solutions be stored in the dark until the time of use. Reconstituted vials must not be shaken. Drug accountability logs must be maintained. .

Preparation

SGN-35 vials are provided via single-use containers. Any partially used vials or diluted dosing solutions should be discarded using appropriate institutional drug disposal procedures.

SGN-35 should be reconstituted with the appropriate amount of Sterile Water for Injection, USP. The vial should be GENTLY swirled until the contents are completely dissolved. **The vial must not be shaken or vigorously swirled**; excess agitation may cause aggregate formation. The reconstituted drug product should be inspected visually for any particulate matter and discoloration.

The appropriate amount of reconstituted SGN-35 should be withdrawn from the vial(s) and diluted in an infusion bag containing 0.9% Sodium Chloride Injection, USP.

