Hemoglobin A1c	x												x
Serum β -HCG***	x												
Hep B, C, HIV	x												
Cytokines		x										x	
Neuropathy Questionnaire	x								x			x	
BM Bx	x												x****
FDG-PET/CT and CT CAP	x												x
Echo or MUGA	x												
PFTs	x												

*may be drawn within 24 hours pre-treatment; ** if creatinine >1.5; ***premenopausal females; ****if previously positive

The following applies to patients receiving augmented ICE:

- A CBC and basic metabolic panel will be obtained upon each admission for chemotherapy and a 12-hour urine collection for creatinine clearance will be obtained prior to receiving carboplatin. Other laboratory evaluations during admission for ICE chemotherapy may be performed at the discretion of the inpatient attending physician. When receiving ifosfamide, urine will be monitored for hematuria by urinalysis.

The following will be performed within 21 days following the completion of augmented ICE:

- CT scan of the chest, abdomen, and pelvis
- FDG-PET/CT scan
- Bone marrow biopsy (if BM was involved before treatment and post-ICE PET scan is negative)

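### No glucose test is scheduled at two thirds of the brentuximab doses, although hyperglycemia was dose limiting on this weekly schedule

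*Combined protocol and SAP*

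**What the plan says.** All references are to the combined protocol and SAP.

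- **Testing, main cohort (Section 10.0).** Under "Tests to be performed day 1 of each cycle of brentuximab vedotin" the list includes a comprehensive metabolic panel. Under "Tests to be performed day 8 and 15 of each cycle of brentuximab vedotin" it has only a history and physical exam and "CBC (may be drawn within 24 hours pre-treatment".
- **Testing, expansion cohort (Section 10.0.1).** The same two lists apply to three cycles. In both sections the calendar agrees with the lists.
- **Known toxicity (Section 3.0).** In the phase I study of weekly dosing, "the dose limiting toxicities were diarrhea and hyperglycemia". The maximum tolerated dose was 1.2 mg/kg, which is the dose used here.
- **Dose rule (Section 5.0).** "The following table describes the recommended dose modifications for study treatment-associated toxicity". For a grade 3 non-hematologic event the dose is held until recovery. For grade 4 it is held and then reduced to 0.8 mg/kg, or treatment stops. Footnote a makes one exception: "Patients who develop Grade 3 or 4 electrolyte laboratory abnormalities may continue study treatment without interruption".
- **Other glycemic measures.** "Hemoglobin (Hgb) A1c" is in the pretreatment list of Section 8.0. "Hemoglobin A1c" appears again in both calendars, in the column after the last dose. A fingerstick glucose is taken at the PET/CT visit.
- **Toxicity list (Section 11.0).** Eight effects are named for brentuximab. Hyperglycemia is not among them.

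**The concern.** A hold rule works only if something brings the event to notice. Three of the relevant kinds of toxicity are noticed at every dose: diarrhea and neuropathy through the history and examination, and cytopenias through the CBC. Hyperglycemia without symptoms is found by none of these, yet it is one of the two toxicities that Section 3.0 reports as dose limiting on this schedule.

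Two things are at stake. A patient could receive a day 8 or day 15 infusion when the table would have advised waiting. In addition, a rise in glucose that comes and goes between day 1 panels would be missing from the toxicity tabulation for secondary objective 3 (Sections 2.0 and 14.0).

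**Working it through.** The plan states no figure of its own here, so the check is a count from the two calendars in Sections 10.0 and 10.0.1. One assumption is needed: that the comprehensive metabolic panel includes glucose, as such panels normally do. Every day 1 dose is counted as covered, which favors the plan.

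**Step 1: doses without a scheduled glucose.**

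| | Main cohort | Expansion cohort |
|---|---|---|
| Dosing days | 1, 8, 15, 29, 36, 43 | 1, 8, 15, 29, 36, 43, 57, 64, 71 |
| Panel days on treatment | 1, 29 | 1, 29, 57 |
| Doses with a panel | 2 of 6 | 3 of 9 |
| Doses without | 8, 15, 36, 43 = 4 of 6 | 8, 15, 36, 43, 64, 71 = 6 of 9 |

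Both fractions equal two thirds.

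**Step 2: age of the latest panel at those doses, with no cycle delay.**
- Second dose of a cycle: 8 − 1 = 36 − 29 = 64 − 57 = 7 days, with one infusion given since.
- Third dose of a cycle: 15 − 1 = 43 − 29 = 71 − 57 = 14 days, with two infusions given since.

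**Step 3: whether another scheduled test fills the gap.** The calendars place hemoglobin A1c at pretreatment and then in days 44–50 (main) or 72–78 (expansion). The last doses are on days 43 and 71, so the second value comes too late to guide any infusion. The fingerstick at the response PET/CT falls in the same windows. The basic metabolic panel at an augmented ICE admission comes later still, and only in Arm B. None of these precedes a day 8 or day 15 dose.

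**Step 4: whether glucose falls under the hold rule.** The exemption covers electrolytes. Section 8.0 spells these out as Na, K, Cl and CO₂, and glucose is not one of them. A grade 3 or 4 glucose abnormality attributed to treatment therefore stays under the non-hematologic row.

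**Step 5: effect and volume of the fix.** With glucose on days 8 and 15, coverage becomes 6 of 6 and 9 of 9. Section 3.0 gives 37 of 46 main-cohort patients accrued by April 2013, so 46 − 37 = 9 remained, plus 20 in the expansion. Added tests, if every dose is given: 9 × 4 + 20 × 6 = 36 + 120 = 156. Patients enrolled but still on brentuximab at that time would add a few.

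**The case against.** The strongest reply is that this is a preference about testing frequency. The plan has chemistry every cycle, a clinical visit and CBC before every infusion, and hemoglobin A1c before and after treatment. The dose table is a recommendation, and nothing bars an unscheduled glucose. Section 3.0 does not say how often hyperglycemia occurred, at which dose, or whether it was silent. The pharmacy manual in Appendix 1 is not reproduced and may say more. Most of this stands, and it is why the point is put as an improvement. It does not remove the gap: a toxicity the protocol itself reports as dose limiting has no scheduled check before most doses.

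The remedy also has drawbacks. More holds could slightly reduce brentuximab exposure before the response PET. Section 5.0 allows for delay only at the start of a cycle and does not say whether a held day 8 or day 15 dose is skipped or made up. That second gap already exists for any hold triggered by a CBC, so the glucose test does not create it. Finally, Section 14.0.1 has the two cohorts analyzed together, and later patients would be tested more closely than the first 37. This is a real cost and has to be reported.

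A reader might extend the point to liver and renal abnormalities, and so ask for a full panel at every dose and another after treatment. The documents do not support that. Neither the brentuximab studies in Section 3.0 nor the list in Section 11.0 names a hepatic or renal toxicity, and Section 6.1 already limits bilirubin and creatinine at entry. These additions are optional.

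**Conclusion.** The point holds for glucose. Two thirds of planned doses in each cohort have no scheduled glucose, and at those doses the latest scheduled value is 7 or 14 days old. This rests on the calendars as printed, on the panel including glucose, and on cycles running without delay.

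A reader might infer that patients on this trial are likely to be dosed through severe hyperglycemia, or that the hold rule cannot work. Neither follows. With no frequency, duration or dose level given, the number of patients affected cannot be estimated, and its absence from the Section 11.0 list is compatible with the event being uncommon. The rule can still be applied to any abnormality found by symptoms, by unscheduled testing or at the next day 1 panel.

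The gap does not touch the primary endpoint, the two-stage design, the requirement of 7 of 46 normalizations after brentuximab alone, or the neuropathy stopping rule. It is a modest safety improvement at low cost, and the design is not in error.

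**What to change.** For remaining main-cohort patients and all expansion patients:

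1. Add a serum glucose to the CBC draw on days 8 and 15 of each cycle, in Sections 10.0 and 10.0.1 and both calendars, using the CBC's 24-hour window.
2. Require the result to be reviewed before infusion, so that the existing Section 5.0 rule can be applied.
3. Repeat a high value before holding a dose, because these draws are not stated to be fasting.
4. Add hyperglycemia to the brentuximab list in Section 11.0.
5. When toxicities are tabulated, give the days on which glucose was measured and note that testing became closer part-way through the main cohort and throughout the expansion.

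The cost is an amendment to the schedule and one more test on blood already being drawn: 4 per main-cohort patient and 6 per expansion patient. There would be a short wait for the result and possibly a few more held doses. Glucose events would be detected more fully in about 29 later patients (9 + 20) than in the 37 already accrued, so a comparison of hyperglycemia between two and three cycles would need that caveat. No new visit, staff or procedure is needed.
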